Protocol Amendment Summary of Changes

Amendment 1 (18 JUL 2023)

This amendment/modification is considered to be non-substantial based on the relevant criteria of the European Union clinical trial legislation.

Overall Rationale for the Amendment

Section # and Name	Description of Change	Brief Rationale
9.4 Interim Analysis	Text added to describe the possibility of conducting an interim analysis during the ongoing study. Original text of this section ("No formal interim analysis using unblinded data is planned for this study, due to the short study duration" deleted.	Depending on recruitment progress, an interim analysis may be performed using the data of all study participants having either regularly completed or prematurely discontinued study intervention at a certain cutoff date, when a minimum of 80% of patients are evaluable. The further study conduct or study design will not be affected by the results of the interim analysis.
Throughout the document	Minor mainly editoral clarifications	

Tab	ole of contents	
Titl	e Page	1
Doc	ument History Table	2
Pro	tocol Amendment Summary of Changes	2
Tab	le of Tables	6
Tah	le of Figures	6
List	of Abbraviations	
LISU		/
1 1 1	Protocol summary	.10
1.1	Synopsis	13
1.3	Schedule of activities (SoA)	14
2	Introduction	16
2.1	Study Rationale	16
2.2	Background	16
	2.2.1 Disease Background	16
	2.2.2 Current Treatment Options and Unmet Medical Need	16
	2.2.3 Rationale for IRAK4 inhibitors as an AD treatment option	18
• •	2.2.4 Zabedosertib (BAY 1834845)	18
2.3	Benefit/risk assessment	19
	2.3.1 Risk Assessment	19
	2.3.3 Overall Benefit/Risk Conclusion	22
3	Objectives, Endpoints, and Estimands	23
3.1	Objectives, Endpoints, and Estimated	23
3.2	Estimand	24
4	Study Design	26
4.1	Overall Design	26
4.2	Scientific Rationale for Study Design	27
4.3	Participant Input into Design	27
4.4	Justification of Dose	28
4.5	End of Study Definition	28
5	Study Population	29
5.1	Inclusion Criteria	29
5.2	Exclusion Criteria	31
5.3	Lifestyle Considerations	34

HCV	henatitis C virus
HDL	high-density lipoprotein
HROoL	health-related quality of life
HIV	human immunodeficiency virus
HRT	hormonal replacement therapy
hsCRP	high sensitivity C-reactive protein
IB	investigator's brochure
IBD	inflammatory bowel disease
ICF	informed consent form
ICH	International Council for Harmonisation of Technical Requirements for
len	Pharmaceuticals for Human Use
ICU	intensive care unit
IEC	independent ethics committee
In	immunoglobulin
IS II	interleukin
IMO	imiquimod
INIR	international normalized ratio
IPS	linopolysaccharide
IR AKA	interleukin1 recentor-associated kinase 4
IRR	institutional review board
	intrauterine device
IRT	Interactive Response Technology
IAK	Ianus kinase
I DH	lactate dehydrogenase
	lower limit of quantification
M&S	Modelling and Simulation
MCP mod	Multiple Comparisons Procedure combined with modeling
MDRD	modification of diet in renal disease
MedDR A	Medical Dictionary for Regulatory Activities
MME	myconhenolate mofetil
MTX	methotrexate
NRS	numerical rating scale
NYHA	New York Heart Association
OATP	organic-anion-transporting polypeptides
PCR	polymerase chain reaction
PD	pharmacodynamic(s)
PE	physical examination
PG	pharmacogenetic(s)
PID	participant identification
РК	pharmacokinetic(s)
PMDA	Pharmaceuticals and Medical Devices Agency
popPK	population pharmacokinetics
PPS	per protocol set
PT	preferred term
Q4	fourth quarter
QC	quality control
QD	once daily
q.i.d.	4 times daily

Clinical Study Protocol Amendment 1 BAY 1834845 / 22158

Page: 9 of 93

quality of life
software environment for statistical computing and graphics
rheumatoid arthritis
ribonucleic acid
serious adverse event
safety analysis set
statistical analysis plan
Statistical Analysis System
severe acute respiratory syndrome coronavirus 2
schedule of activities
standard-of-care
System Organ Class
standard operating procedure
tuberculosis
total bilirubin
topical calcineurin inhibitor
topical corticosteroids
treatment-emergent adverse event(s)
treatment-emergent adverse events of special interest
treatment-emergent serious adverse event
toll like receptor
thyroid stimulating hormone
thymic stromal lymphopoietin
upper limit of normal
validated Investigator Global Assessment for Atopic Dermatitis
vIGA-AD of 0 or 1 with at least a 2-grade reduction from baseline
verbal rating scale
white blood cell
women of child-bearing potential

Page: 10 of 93

1 Protocol summary

1.1 Synopsis

Protocol Title:

A randomized, placebo-controlled, double-blind, parallel-group, multicenter Phase 2a study to investigate efficacy and safety of zabedosertib (BAY 1834845) for the treatment of adult patients with moderate-to-severe atopic dermatitis

Short Title:

Proof-of-concept of efficacy and safety of zabedosertib in the treatment of moderate-to-severe atopic dermatitis in adults

Regulatory Agency Identifier Number(s):

EudraCT Number: 2022-000520-38

Envisaged indication:

Moderate-to-severe atopic dermatitis in adults

Rationale:

Based on scientific considerations and preclinical observations, zabedosertib may provide a safe and effective treatment option for atopic dermatitis (AD) by its anti-inflammatory properties.

The aim of this Phase 2a study is to explore for the first time whether the interleukin-1 receptorassociated kinase 4 (IRAK4) inhibitor zabedosertib can safely provide a therapeutic benefit in patients with moderate-to-severe AD and to achieve a proof of concept for further development steps of the compound (or the compound class).

Objectives, Endpoints and/or Estimands:

Objectives	Endpoints
 Primary objectives To assess the efficacy of zabedosertib vs. placebo in adult patients with moderate-to-severe atopic dermatitis (AD) with inadequate response to topical corticosteroids or if topical treatments are medically not advisable 	 Primary endpoint: Achievement of 75% reduction from baseline in the Eczema Area and Severity Index (EASI 75 response) at Week 12 (Day 84) Primary endpoint is the composite variable defined as follows: an EASI 75 response at Week 12 (Day 84), no stop of study intervention for reasons related to lack of efficacy, no rescue medication use during the 4 weeks before Day 84 and no use of systemic AD treatment
	 Secondary endpoints: Percent change from baseline in EASI at Week 12 (Day 84) Achievement of EASI 50 response at Week 12 (Day 84) Achievement of EASI 90 response at Week 12 (Day 84) Achievement of a vIGA-AD response (score 0 or 1 and ≥ 2 points improvement) at Week 12 (Day 84) Absolute change from baseline in body surface area (BSA) affected by AD at Week 12 (Day 84) Absolute values and percent change of weekly average of the Peak Pruritus 0-10 NRS score from baseline at Week 12 (Day 84) Achievement of a ≥ 4 point-improvement (reduction) in the weekly average of the Peak Pruritus 0-10 NRS score ≥ 4 at baseline
 Secondary objectives To assess the safety and tolerability of zabedosertib vs. placebo 	 Secondary endpoints: Frequency and severity of treatment-emergent adverse events (TEAEs) Other safety endpoints: Frequency and severity of TEAEs of special interest Changes in vital signs from baseline Changes in clinical laboratory test results from baseline (e.g., chemistry, lipid panel, hematology, urinalyses) Changes in electrocardiogram (ECG) parameters from baseline and frequency of ECG findings

Exploratory objectives and other pre-specified endpoints are listed in Section 3.

Overall Design Synopsis:

Disclosure Statement: This is a randomized, placebo-controlled, double-blind, parallel-group multicenter, Phase 2a study to investigate efficacy and safety of zabedosertib for the treatment of adult patients with moderate-to-severe atopic dermatitis.

Short Summary

The purpose of this study is to assess the efficacy and safety of zabedosertib compared with placebo in participants with moderate-to-severe AD. The study consists of an up to 28-day screening period (Visits 1 and 2), a 12-week intervention period consisting of 5 visits (Visits 3 to 7), and a 4-week follow-up (FU) period with one visit (Visit 8).

A total of 72 participants are planned to be randomly allocated to 1 of the 2 treatment groups with a 2:1 allocation ratio to achieve a total of 57 participants valid for efficacy analysis:

Zabedosertib at a dose of 120 mg BID:	48 randomized / 38 valid for the efficacy analysis
Matching placebo BID:	24 randomized / 19 valid for the efficacy analysis.

Efficacy parameters will be assessed prior to study intervention, during the 12-week intervention period and at follow-up according the Schedule of Activities (SoA).

All participants will be closely monitored for safety throughout the study.

To gain most accurate dosing data and to ensure adherence to study intervention, the data of participant's daily intake of study intervention will be collected as daily questions on an electronic patient handheld device. Participants are required to use additive-free emollients twice a day throughout the study. Participants will be reminded once a week about this requirement by the electronic hand held device.

Blood sampling for pharmacokinetic and pharmacodynamic evaluations will be obtained in accordance with the SoA.

At selected study sites in a subset of participants, skin biopsy samples will be taken for the assessment of gene expression and immunohistochemistry as indicated in the SoA.

Number of Participants:

Approximately 72 participants will be randomly assigned to the study to obtain 57 evaluable participants overall (2:1 randomization zabedosertib versus placebo).

Study Arms and Duration:

The total study duration per participant will be 17 to 20 weeks (approximately 140 days), with 8 study visits at intervals of 8 to 28 days with 2 study arms:

Zabedosertib at a dose of 120 mg BID orally:	48 randomized participants
Matching placebo BID orally:	24 randomized participants.

Dose changes and/or adjustments are not planned. Decisions regarding dose interruptions will be made by the investigator in consultation with the Medical Monitor based on the clinical evaluation of the participant.

Data Monitoring/Other Committee: No

Page: 13 of 93

1.2 Schema

Figure 1–1: Detailed schema

S= screening, R= randomization, V= visit, D= day, EOT= end of treatment, EOS= end of study

Page: 14 of 93

1.3 Schedule of activities (SoA)

		Scree	ning	Inter	venti	on per	riod		Follow-up
	(For footnotes, see next page.)			Randomization		•		EOT ¹	Days after last dose 28 ²
	Visit	1	2	3	4	5	6	7	8 (EOS)
	Day	-28 to-14	-8 +1	1	14 ±2	28 ±2	56 ±3	84 ±3	112 ±3
	General Informed Consent	•							
	Consent Skin Biopsy ³	•							
	Consent Photography ³	•							
	Demography	•							
5	Quantiferon TB Gold Plus test	•							
io	HIV, hepatitis B and C	•							
iat	SARS-CoV-2 RNA test ⁴		٠						
nit	Medical history / history of AD	•							
	Prior medication / prior AD therapy	•		•					
	Height	•							
	Weight	•		•	٠	•	•	٠	•
	Check of in-/exclusion criteria	•	٠	•					
	Randomization			•					
2	IRT registration	•		•	•	•	•	•	
atio	Study intervention dispensation			•	•	•	•		
i č	Study int. return / accountability				•	٠	•	٠	
ea	Study intervention intake			•→	or	ngoing		→	
S	Enter intervention intake into			·	or	ngoing		→	
	eDiary					 			
	Concomitant medication	•	٠	•	•	•	•	•	•
	ClinROs								
>		•		•	•	•	•	•	•
ac	- VIGA-AD	•		•	•	•	•	•	•
ЦС	- BSA affected by AD	•		•	•	•	•	•	•
Ш	 Dispense and training of patient handheld device 		•						
	- Daily Peak Pruritus 0-10 NRS ⁶		←		ong	going -			→
	- Return handheld device								•
	Other procedure: photograph ⁰			•				•	•
	Complete physical examination	•		•				•	٠
	Symptom-directed PE/inspection		•		•	•	•		
>	AE/SAE assessment	•8	• ⁸	•	٠	•	٠	٠	•
etj	AESI assessment	•8	• ⁸	•	٠	•	٠	٠	•
Safe	Pregnancy test – S(erum) / U(rine)	●s	●S	●U	●U	●U	●U	●U	●S
	Safety panel (central lab)9	•	● ¹⁰	•	•	•	•	•	•
	Lipid profile (central lab)			•				٠	
	Urinalysis	•	● ¹⁰	•		٠		٠	•
	12-lead ECG ¹¹	•			•			•	•
_	Vital signs	•	•	•	•	٠	•	•	•
ð	BM blood samples ¹²			•				•	
3	BM on-study skin biopsy ^{13,14}			•				•	
đ	PK blood sample			●15	● ¹⁶	●16	●16	●15,16	

Footnotes for schedule of activities (see next page)

Footnotes for schedule of activities

AD = atopic dermatitis; AE(SI) = adverse event (of special interest); BM = biomarker; BSA = body surface area; ClinROs = clinician-reported outcomes; CRP = C-reactive protein; EASI = Eczema Area and Severity Index; ECG = electrocardiogram; eDiary = electronic diary (= patient handheld device); EOS = end of study; EOT = end of treatment; HIV = human immunodeficiency virus; IRT = Interactive Response Technology; NRS = numerical rating scale; PD = pharmacodynamc(s); PE = physical examination; PK = pharmacokinetic(s); PRO = patientreported outcome; RNA = ribonucleic acid; SAE = serious adverse event; SARS-CoV-2 = severe acute respiratory syndrome coronavirus 2; v = visit; vIGA-AD = validated Investigator's Global Assessment for Atopic Dermatitis

Early Discontinuation: Visit 7 (EOT) and Visit 8 (EOS) assessments should be performed Performed 28 days after last dose of study intervention

Optional, should be obtained for participants taking part in the skin biopsy subgroup or the photograph subgroup. Consent can be obtained up to Visit 3.

In exceptional cases, e.g., if test results are not available in time, SARS-CoV-2 test (PCR test or similar test) may be performed locally.

First dose of study intervention should only be taken after all baseline assessments are completed. Daily assessment should start 7 days before randomization visit.

At select study sites (optional): Photographs of a representative area of AD involvement (e.g., the lesioned area used for EASI assessments). Instructions for taking the photographs will be provided in a photography manual.

Only (S)AEs which are related to protocol-required study procedures should be recorded before start of study intervention (all other events should be recorded as medical history).

- Safety panel (central lab) will include parameters listed in Appendix 10.2 (Table 10-1)
- Only CRP, blood count, and urinalysis must be re-assessed at Visit 2 to rule out asymptomatic infections; further lab values only in case results from screening lab (Visit 1) require re-testing for eligibility or clinically indicated control-analyses.
- May be performed + 3 days of visit. All ECG reports are to be assessed for clinical significance by a physician.
- Blood samples (plasma and whole blood) for molecular biomarkers (optional analysis) In total 2, BM samples will be collected: 1x biomarker blood plasma and 1x biomarker whole blood. See Table 8–1 for further details to BM samples.
- At select study sites (optional): Skin lesion biopsy samples (2 x 3 mm punch biopsies per timepoint) in approximately 40 participants for assessment of gene expression (e.g., inflammation and skin barrier markers) and immunohistochemistry (e.g., immune cells; optional analysis). Two BM samples each at baseline and at EOT will be collected: biomarker on-study skin biopsy for mRNA expression and 1x biomarker on-study skin biopsy for IHC expression. See Table 8–1

for further details to BM samples.

Optional procedure requiring a separate informed consent

Post-morning dose blood samples for pharmacokinetics between 0.5 to 1.5 hours post-dose, and between 2 to 5 hours post-dose with at least 1 hour difference between the 2 post-dose samples. NOTE: At visits with PK, study drug intake of the morning dose should occur at the study site. The participants should bring their handheld devices to these visits as well.

Blood samples for pharmacokinetics should be taken pre-dose. NOTE: At visits with PK, study drug intake of the morning dose should be taken at site. The participants should bring their handheld devices to these visits as well.

2 Introduction

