6.1 Study Intervention(s) Administered

The study interventions administered for this trial are summarized in Table 6–1.

Intervention Label	Zabedosertib	Placebo
Intervention Name	Zabedosertib; IRAK4 inhibitor	Placebo (matching to zabedosertib)
Intervention Description	120 mg tablet orally twice daily (BID) for 12 weeks	1 placebo tablet orally twice daily (BID) for 12 weeks
Туре	Drug	Drug
Dose Formulation	Tablet	Tablet
Unit Dose Strength(s)	120 mg	not applicable
Dosage Level(s)	120 mg BID	BID dosing
Route of Administration	Oral	Oral
Use	Experimental drug	Control
Packaging and Labeling	Study intervention will be provided in HDPE bottles closed with child-resistant screw cap. Each bottle will be labeled as required per country requirement.	

Table 6–1: Study interventions

HDPE = high-density polyethylene; IRAK4 = interleukin1 receptor-associated kinase 4

Tablets containing zabedosertib or corresponding placebo are identical in appearance (size, color, shape). In order to remain blinded, study interventions will be packaged in bottles labeled with a unique number which will be pre-printed on each bottle.

All participants will take study intervention (zabedosertib or matching placebo) BID (morning and evening doses) approximately the same time each day 12 hours apart.

Tablets are not to be broken, halved or crushed; they should be swallowed as a complete unit with water. Daily tablet intake should be done at home. At visits with PK, study drug intake of the morning dose should occur at the study site.

If a dose of study intervention has been missed:

- If up to 6 hours have passed since the dose was due, it should be taken immediately
- If more than 6 hours have passed since the dose was due, the dose should be skipped, and the next dose should be taken according to the regular schedule.

Arm Title	Zabedosertib	Placebo
Arm Type	experimental	placebo
Arm Description	Participants will receive 120 mg zabedosertib BID for 12 weeks.	Participants will receive an equivalent number of tablets of matching placebo for 12 weeks.
Associated Intervention Labels	zabedosertib 120 mg	Placebo

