Prior and concomitant therapies not permitted in this study are listed in Section 5.2, exclusion criteria. Therapies listed in the exclusion criteria are also prohibited during the study (exception: TCSs and TCIs may only be used as rescue medication).

In addition, the use of antihistamines and live vaccination are not allowed during the study.

If the participant took a prohibited medication or used a prohibited non-drug therapy for any reason, the investigator should consult with the sponsor to determine if the participant should be withdrawn from study intervention and/or the study.

For the purpose of efficacy analysis, participants receiving any pharmacologically active nonstudy medication or phototherapy for AD will be considered as treatment failures after the start of such medication, except for the use of defined topical rescue medication up to/including Week 8. Whenever possible, efficacy and safety assessments according to Visit 7 (EOT) should be conducted immediately before administering any systemic medications for AD or initiation of phototherapy (= SoC). For zabedosertib, a wash-out period of 7 days (approximately 5 half-lives) is recommended, because there is no experience or data with a combination of zabedosertib and systemic AD treatment.

SoC should be reserved for participants who do not respond adequately to topical treatment (at least 7 days of use). If a participant receives SoC treatment with systemic corticosteroids or non-steroidal systemic immunosuppressive drugs (cyclosporine, methotrexate, MMF, azathioprine, baricitinib etc.) dupilumab, tralokinumab or initiation of phototherapy, study intervention has to be discontinued and EOT assessments including FU visits performed.

7 Discontinuation of Study Intervention and Participant Discontinuation/Withdrawal

Discontinuation of specific sites or of the study as a whole are detailed in Appendix 1 (Section 10.1.11).

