4.4.7 Pharmacokinetics

All PK analyses will be performed on the PKS.

Plasma samples will be collected for measurement of plasma concentrations of zabedosertib and its metabolite BAY 2822815 at Day 14 (Visit 4), Day 28 (Visit 5), Day 56 (Visit 6), Day 84 (Visit 7) pre-dose as well as between 0.5 to 1.5 hours and between 2 to 5 hours post-dose at Day 1 (Visit 3) and Day 84 (Visit 7).

The following statistics will be reported for plasma concentrations of zabedosertib and its metabolite at each visit (and time point if applicable): geometric mean, geometric standard deviation (re-transformed standard deviation of the logarithms) and geometric coefficient of variation (CV), arithmetic mean, standard deviation and CV, minimum, median, maximum value and the number of measurements as well as the number of measurements \geq limit of quantification (LLOQ). Means at any visit will only be calculated if at least 2/3 of the individual data were measured and were above LLOQ. Otherwise only minimum, median and maximum will be presented. For the calculation of the mean value, standard deviation and median a data point below LLOQ will be substituted by one half of this limit. In tables showing mean values, where values below LLOQ are included in the calculation of mean values, these means will be marked.

Furthermore, geometric means including one standard deviation range will be plotted for zabedosertib and its metabolite. The post-dose time between 0.5 to 1.5 hours post-dose will be presented at 1hour post-dose and the time between 2 to 5 hours will be presented at 3.5 hours post-dose on the x-axis.

Box plots including geometric mean for the concentration of zabedosertib and its metabolite BAY 2822815 will be presented as well.

Furthermore, individual plots of zabedosertib and its metabolite will be presented.

Pre-dose PK concentrations will be considered valid for inclusion into summary statistics if there were 8-16 hours between the last documented tablet intake before pre-dose PK sample collection and the pre-dose PK sample collection. Post-dose PK concentrations will be considered valid for inclusion into summary statistics if a tablet intake in the morning of the post-dose PK sample collection was documented. Furthermore, pharmacokinetic values might be flagged as invalid by the pharmacokinetic experts to be excluded from the calculation of summary statistics if applicable.

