- ALT or AST > 3 x ULN and INR > 1.5 x ULN (INR > 1.5 x ULN is only relevant if the participant is not on Vitamin K antagonist, new oral anticoagulants (NOACs) or heparin.)
- ALT or $AST > 5 \times ULN$ for more than 2 weeks
- ALT or $AST > 8 \times ULN$

Abnormalities with respect to neutrophil counts:

- Absolute neutrophil count < 500 cells/ μ L,
- Absolute neutrophil count 500 to < 1000 cells/ μ L,
- Absolute neutrophil count 1000 to < 1500 cells/ μ L.

Abnormalities with respect to creatinine kinase:

- Creatine kinase (CK) >ULN to < 5 x ULN,
- Creatine kinase (CK) 5 to 10 x ULN,
- Creatine kinase (CK) > 10 x ULN.

Vital signs

Vital signs will consist of single measurements of systolic blood pressure, diastolic blood pressure, pulse rate and body temperature. Vital signs including height (only summary statistics for the baseline value), weight and BMI will be summarized descriptively by parameter including absolute changes from baseline. Arithmetic mean plots including standard deviation over time will be presented. In addition, box plots including arithmetic means over time will be presented for changes from baseline. Individual plots over time will be generated.

Electrocardiogram

Single 12-lead ECG will be obtained locally.

ECG parameters (PR, QRS, QT, corrected QT intervals (according to Bazett's formula) and the ventricular rate) will be summarized descriptively by parameter including absolute changes from baseline. Arithmetic mean plots including standard deviation over time will be presented. In addition, box plots including arithmetic means over time will be presented for changes from baseline. Individual plots over time will be presented.

Furthermore, frequency tables will be presented for corrected QT intervals for absolute values with the following categories:

• >450 to 480 msec, >480 msec to 500 ms, >500 msec,

and absolute change from baseline with the following categories:

• >30 to 60 msec, >60 msec.

A frequency table will be provided for the ECG findings assessed by the investigator, and for overall interpretation of ECGs (normal; abnormal, clinically insignificant; abnormal, clinically significant).

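### The Day 84 ECG may be recorded up to 3 days after the last dose, and the SAP does not separate such late ECGs in the Day 84 QTc and heart-rate summaries

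*Protocol*

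**What the plan says.** - **When ECGs are taken.** Protocol Section 1.3 schedules a 12-lead ECG at Visit 1 (screening), Visit 4 (Day 14), Visit 7 (Day 84, end of treatment) and Visit 8 (28 days after the last dose). The footnote to that row allows flexibility: "May be performed + 3 days of visit. All ECG reports are to be assessed for clinical significance by a physician". It applies to all four visits alike.
- **When dosing stops.** Treatment is described in Section 6.1 as "120 mg tablet orally twice daily (BID) for 12 weeks". The schedule shows drug dispensed at Visits 3 to 6 only and returned at Visit 7. Visit 7 is also a PK visit, and the PK footnote says: "At visits with PK, study drug intake of the morning dose should occur at the study site". That on-site morning tablet is therefore the last dose for someone who completes treatment.
- **How long the participant is on site.** At Visit 7 a second post-dose PK sample is due "between 2 to 5 hours post-dose with at least 1 hour difference between the 2 post-dose samples". SAP 4.4.7 confirms post-dose sampling on Day 84.
- **How fast the drug leaves.** For starting systemic AD therapy, protocol Section 6.9.3 states that "a wash-out period of 7 days (approximately 5 half-lives) is recommended". Section 7.1 repeats this.
- **How ECGs are analysed.** SAP 4.5.3 summarises PR, QRS, QT, QTcB and ventricular rate with changes from baseline, and adds that "frequency tables will be presented for corrected QT intervals for absolute values with the following categories". Change categories of more than 30 to 60 msec and more than 60 msec follow. SAP 4.1.1 presents results by visit, with Day 84 (Visit 7) labelled separately from follow-up. Neither section limits the time between last dose and ECG.

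**The concern.** At Day 14 a 3-day delay does no harm, because the participant keeps taking tablets. At Visit 7 the same delay moves the ECG into washout. Nothing in the SAP then tells an ECG taken 2 hours after a dose from one taken 3 days after the last dose. Both contribute to the Day 84 mean change and to the box plots.

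If zabedosertib has a concentration-related effect on QTc or heart rate, late ECGs pull the Day 84 estimate towards no effect, which is the unwelcome direction for a safety summary. Day 84 is the only ECG under dosing after Day 14. The longest earlier exposure at this dose cited in protocol Section 4.4 is 8 weeks, so it is also the ECG that speaks to longer treatment. ECG change from baseline is a listed safety endpoint (protocol Section 3.1).

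**Working it through.** The documents give no residual-drug figure, so there is none to reproduce. The check uses their stated inputs.

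**1. Half-life.** Protocol 6.9.3 and 7.1: 7 days is about 5 half-lives.

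t½ = 7 × 24 / 5 = 33.6 h (1.4 days)

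**2. Latest Visit 7 ECG.** The last dose is the on-site morning tablet on the visit day. An ECG at +1, +2 or +3 days comes about 24, 48 or 72 h later.

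**3. Fraction remaining,** assuming mono-exponential decline: 2^(−t / t½). Because the half-life is only approximate, the count of half-lives in 7 days is varied from 4.5 to 5.5.

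| Half-lives in 7 days | t½ (h) | 24 h | 48 h | 72 h |
|---|---|---|---|---|
| 4.5 | 37.3 | 64% | 41% | 26% |
| 5 | 33.6 | 61% | 37% | 23% |
| 5.5 | 30.5 | 58% | 34% | 20% |

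Measured against the 12-hour trough instead of the level at the last dose, the 72 h figure is 2^(−60/33.6) = 29%.

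**4. What this does to an effect.** If the effect is proportional to concentration (an assumption), a hypothetical 10 msec effect would read as about 6, 4 and 2 msec at 24, 48 and 72 h. In a group mean the loss depends on the share f of participants whose ECG is late. If all late ECGs were at the full 72 h, the mean would keep 1 − f × (1 − 0.226) = 1 − 0.774f of the effect. For assumed values f = 10%, 25% and 50% this is 92%, 81% and 61%. The documents give no value for f.

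**5. Day 14 under the same model.** After 13 days of dosing (312 h), accumulation has reached 1 − 2^(−312/33.6) = 99.8% of steady state. Dosing continues through any delay, so this ECG carries the full proportional effect.

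**6. Does another SAP rule catch late ECGs?**
- The Table 8-3 visit windows (SAP 8.4.1) cover efficacy assessments only.
- The 3-day limit in SAP 4.1.2 concerns end-of-treatment values after early discontinuation, and would itself accept a value at 3 days.
- SAP 4.4.7 (8 to 16 h for pre-dose PK) and 4.4.8 (3 days for biomarkers) set time-since-dose rules for other data. None is set for ECGs at a regular Visit 7.

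**The case against.** **The Day 14 ECG already answers the question.** Under proportionality, step 5 shows the full effect is captured there. This stands and is the main reason the point is small. What is left for Day 84 is confirmation at the end of treatment, and any effect that emerges only with longer exposure, for which the documents give no specific reason.

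**The 23% is a worst case.** The footnote is permissive, and participants are on site for hours after the dose that day. A reader might infer that half of the ECG data under dosing is washout data. That would require every Visit 7 ECG to be delayed, and nothing in the documents shows that even one is.

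**The documents never call this ECG on-treatment.** The label is Day 84 (Visit 7). A reader might infer a contradiction between protocol and SAP, but there is none. A 3-day tolerance matches the SAP's handling of early end-of-treatment values and biomarkers, and adverse events count as treatment-emergent for 7 days. The gap is a missing distinction within one summary.

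**No ECG-concentration pairing is planned.** A reader might infer that a late ECG breaks a match with the Visit 7 PK samples. No section links the two, and exposure-response work is optional under a separate plan (protocol 8.5.2).

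**Excluding late ECGs would do harm.** This stands. A rule dropping all ECGs taken after the last-dose day would also remove early-discontinuation ECGs that SAP 4.1.2 can keep. It could take a large QTc value out of the category tables.

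**The prior expectation is low.** Protocol 8.4.6 reports no interaction with cardiac ion channels and no clinically significant ECG findings in two earlier studies, and pulse rate is measured at every visit. This lowers the likely effect but is no reason to dilute the check.

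**Conclusion.** The point holds as a minor gap. The ECG window extends past the end of dosing at Visit 7, and the SAP has no means of separating late ECGs in the Day 84 summaries of QTcB and ventricular rate. For an affected ECG, about 61%, 37% or 23% of drug remains at 1, 2 or 3 days, with 20% to 26% at 3 days. Any dilution of the group mean scales with the unknown share of late ECGs, and is nil if all were taken on the visit day.

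The size rests on an approximate half-life taken from a washout recommendation, on mono-exponential decline, and on an effect proportional to parent-drug concentration. No half-life is given for metabolite M-5. The documents do not support reading this as a failure of the trial's ECG safety assessment: Day 14 is unaffected, and the analysis is descriptive.

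**What to change.** 1. **Schedule of activities, ECG footnote.** Exclude Visit 7 from the 3-day allowance for participants completing treatment. Record that ECG on the visit day after the on-site morning dose, while the participant is present for the post-dose PK samples. Early-discontinuation ECGs stay as they are.
2. **SAP 4.5.3.** Derive the number of days from last dose to the Visit 7 ECG and flag ECGs taken after the last-dose day. Keep every ECG in the QTc category tables and the any-time-point findings table. Add one Day 84 change-from-baseline summary restricted to ECGs taken on the last-dose day.

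**Cost.** Some scheduling flexibility at Visit 7 is lost and one table is added. The derivation needs only the ECG date and the last-dose date.

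**Timing.** SAP 4.7 puts about 90% of participants as randomised by 02 August 2023. For a participant starting on that date, Day 84 falls on 24 October. Adding the 3-day visit window and the 3-day ECG allowance gives 30 October, one day before the SAP date of 31 October 2023. For participants already past Visit 7, only item 2 applies. Item 1 serves any remaining participants and a successor protocol.
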